11.8. Discontinuation of Study Treatment

A subject *must* permanently discontinue DAC HYP for any of the following reasons:

- The subject becomes pregnant. Study treatment must be discontinued immediately. Report the pregnancy according to the instructions in Section 15.5.4.
- The subject experiences a hypersensitivity or suspected allergic reaction (e.g., anaphylaxis and anaphylactoid reactions) to study treatment.
- The subject develops a chronic viral infection (e.g., hepatitis C, HIV).
- The subject develops elevated LFTs that meet any of the following criteria:
 - ALT/SGPT or AST/SGOT $>5\times$ ULN that is confirmed by a repeat test performed within 1 week
 - ALT/SGPT or AST/SGOT $>3\times$ ULN with concomitant elevation of total bilirubin $>2\times$ ULN that is confirmed by a repeat test performed within 1 week
 - If a subject has treatment suspended for an LFT elevation and has also had a prior treatment suspension for an LFT elevation during DAC HYP use, DAC HYP must be permanently discontinued unless an alternative explanation for the LFT elevation unrelated to DAC HYP use is clearly identified by the Investigator.
- The subject experiences a cutaneous AE, which the Investigator (in consultation with the *Study Dermatologist*) considers to be a generalized allergic or hypersensitivity reaction to study treatment (see Section 11.7.3).
- The subject experiences inflammatory colitis, except in subjects with mild colitis who require DAC HYP therapy and have a positive benefit-risk profile per Investigator's assessment and the subject's informed decision (see Section 11.7.4).
- The subject requires treatment with any of the disallowed concomitant medications, unless approval is given by the Biogen Medical Director(s) or Advisory Committee. Note: IVMP for treatment of a protocol-defined relapse is allowed as detailed in the protocol (see Section 11.5). Treatment with valproic acid, carbamazepine, lamotrigine, or phenytoin is only allowed under the conditions detailed in the protocol.
- The subject experiences a medical emergency that necessitates permanent discontinuation of treatment.
- The subject desires to discontinue treatment under this protocol.
- At the discretion of the Investigator for medical reasons or for non-compliance.
- Upon confirmatory tests 1 month apart, the subject's hematology results are as follows in the absence of an identified reversible cause by the Investigator (e.g., infection):
 - white blood cell count is <2500 cells/ μ L, or
 - lymphocyte count is <800 cells/ μ L, or

CONFIDENTIAL

The information contained herein may not be used, disclosed, or published without the written consent of Biogen MA Inc.

- platelet count is $<75,000$ cells/ μL
Subjects who meet the above criteria must have study treatment withheld until hematology retest results are available.
- The subject experiences severe depression and/or suicidal ideation. Severe depression is defined as any episode that requires hospitalization, or at the discretion of the Investigator.

Subjects who permanently discontinue DAC HYP treatment should complete all post-treatment safety follow-up evaluations (see Section 14.10).

Subjects who permanently discontinue study treatment may be treated with alternative approved MS therapies according to local practices, and should remain in the study and complete safety follow-up evaluations as described in Section 4.2 and Section 13. However, subjects who desire to discontinue participation in this study or are unwilling or unable to comply with the protocol should be withdrawn from the study and complete an Early Termination Visit. As noted in Table 6 (Footnote 3) and Section 11.9, subjects terminating treatment with an ongoing cutaneous AE require an Unscheduled Dermatology Assessment Visit prior to leaving the study if the subject has not had such a visit in the 4 weeks \pm 4 days prior to leaving the study. If the event is, at the time of termination, a mild or moderate cutaneous AE that is associated with more than 1 systemic symptom or sign, a severe cutaneous AE (with or without systemic symptoms or signs), or a serious cutaneous AE (with or without systemic symptoms or signs), then the assessment should be performed by the *Study Dermatologist*. If the event is considered mild or moderate and is not associated with more than 1 systemic symptom or sign, then the assessment can be performed by the *Study Neurologist* or the *Study Dermatologist*.

The reason(s) for discontinuation of treatment must be recorded in the subject's CRF.

11.9. Withdrawal of Subjects From Study

Subjects must be withdrawn from the study for any one of the following reasons:

- The subject withdraws consent.
- The subject is unwilling or unable to comply with the protocol.
- At the discretion of the Investigator for medical reasons.

Subjects who withdraw from the study should complete the End of Treatment Visit assessments as described in Section 14.10 (subjects should be encouraged to complete all other post-treatment safety follow-up visits). The reason for the subject's withdrawal from the study must be recorded in the subject's CRF.

For subjects with an ongoing mild or moderate cutaneous AE that is associated with more than 1 systemic symptom or sign, severe cutaneous AE (with or without systemic symptoms or signs), or serious cutaneous AE (with or without systemic symptoms or signs), the *Study Dermatologist* should perform an Unscheduled Dermatology Assessment Visit if this visit has not been performed in the 4 weeks \pm 4 days prior to leaving the study (see Section 11.7.3). If the event is considered mild or moderate and is not associated with more than 1 systemic symptom or sign, then the assessment can be performed by the *Study Neurologist* or the *Study Dermatologist*.

CONFIDENTIAL

The information contained herein may not be used, disclosed, or published without the written consent of Biogen MA Inc.

12. EFFICACY, DAC HYP CONCENTRATION, AND [REDACTED] ASSESSMENTS

12.1. Clinical Efficacy Assessments

The following clinical tests/assessments will be performed to assess the efficacy of DAC HYP:

- Relapse Assessment: Subjects who suspect they are experiencing new symptoms or worsening symptoms need to contact the *Study Neurologist* within 48 hours of the onset of the symptoms.
- Refer also to Section 14.6 Unscheduled Relapse Assessment Visit for additional details.
- EDSS [Kurtzke 1983]: Review of EDSS procedures will be performed prior to study start as necessary for training purposes.
- MSFC [Fischer 1999]: Timed 25-Foot Walk, 9HPT with both upper extremities, and PASAT 3
- SDMT: Data will be collected only from subjects enrolled from Study 205MS301, and test performance data will be collected beginning in Week 144 and every 24 weeks thereafter.
- PASAT 3: This test will be performed separately from the MSFC beginning in Week 144 and every 24 weeks thereafter. Data will be collected only from subjects enrolled from Study 205MS301.
- Brain MRI scan with and without Gd (T2 hyperintense lesions, T1 hypointense lesions, Gd+ lesions, brain atrophy).
- Subjects will complete the following questionnaires at various timepoints specified in Section 4.2:
 - EQ-5D quality of life questionnaire (the EQ-5D descriptive system and the EQ-VAS)
 - MSIS-29 (29-item physical and psychological assessment)
 - HRU (hospitalizations, emergency room visits, and unscheduled neurologist visits)
 - Treatment Satisfaction Questionnaire for Medication (with PFS use) or Treatment Satisfaction Survey (with autoinjector use)
 - HRPQ (productivity questionnaire)

Refer to Section 4.2 for the timing of assessments.

CONFIDENTIAL

The information contained herein may not be used, disclosed, or published without the written consent of Biogen MA Inc.

12.2. Pharmacokinetic Assessments

Blood samples will be collected at selected timepoints throughout the study to determine DAC HYP serum concentrations in order to monitor the drug trough level and [REDACTED]

Unscheduled PK/ [REDACTED] Visits

Whole blood samples will be collected at Unscheduled PK/ [REDACTED] Visits for potential determination of DAC HYP serum concentrations in subjects with significant changes in their medical conditions, as assessed by the Investigator. This visit must be approved by the Biogen Medical Director in advance.

Refer to Section 4.2 for the timing of sample collection.

12.3. [REDACTED]

[REDACTED]

[REDACTED]

[REDACTED]

[REDACTED] PK/ [REDACTED]

[REDACTED] PK/ [REDACTED]

12.4. [REDACTED]

[REDACTED]

CONFIDENTIAL

The information contained herein may not be used, disclosed, or published without the written consent of Biogen MA Inc.

13. SAFETY ASSESSMENTS

13.1. Clinical Safety Assessments

The following clinical assessments will be performed to determine the safety profile of DAC HYP:

- Medical history
- Physical and neurological examination
- Vital sign measurements: temperature, pulse rate, systolic and diastolic blood pressure, and respiratory rate (subjects must remain in the same body position quietly for 5 minutes prior to having their pulse and blood pressure taken)
- Weight
- Concomitant therapy and procedure recording
- AE and SAE recording
- Beck Depression Inventory, Second Edition (BDI-II)
- Immunogenicity assessments
- Alcohol Use Disorders Identification Test - Consumption Questionnaire (AUDIT-C)

See Section 4.2 for the timing of assessments.

13.2. Laboratory Safety Assessments

The following laboratory tests will be performed to assess the safety profile of DAC HYP:

- Hematology: hemoglobin, hematocrit, mean corpuscular volume, mean corpuscular hemoglobin, mean corpuscular hemoglobin concentration, red blood cell count, white blood cell count (with differential), and platelet count
- Blood chemistry: sodium, potassium, chloride, total bilirubin, alkaline phosphatase, ALT/SGPT AST/SGOT, lactate dehydrogenase, gamma glutamyl transferase, blood urea nitrogen (BUN), creatinine, and bicarbonate
- Comprehensive hepatic panel (only required for subjects who permanently discontinue dosing due to elevated LFTs as defined in Section 11.7.2). Testing will include screening for the following:
 - hepatitis A, B, C, and E
 - other viral infections: Epstein-Barr virus (EBV), cytomegalovirus (CMV), human herpes virus 6 (HHV-6), varicella zoster virus (VZV), herpes simplex virus (HSV), and Parvovirus B19
 - gamma-globulins, including IgG levels

CONFIDENTIAL

The information contained herein may not be used, disclosed, or published without the written consent of Biogen MA Inc.

- autoantibodies: antinuclear antibody (ANA), anti-smooth muscle antibody (anti-SM), anti-liver/kidney microsome-1 antibody (anti-LKM1), antimitochondrial antibody (AMA), and anti-soluble liver antigen (SLA)

Additional testing may be performed based on results of the above testing or the subject's clinical history. Additional hepatic assessments should be performed according to local standard of care.

- Thyroid function panel, including TSH and T4
- Urinalysis: protein, blood, glucose, ketones, nitrite, leukocytes, pH, specific gravity by dipstick and microscopy
- Urine pregnancy testing
- Skin biopsy (only required for subjects who experience cutaneous AEs reported as serious or severe as defined in Section 11.7.3)

Refer to Section 4.2 for the timing of assessments.

13.3. Study-Specific Safety Assessments

Blood serum collection for binding and neutralizing anti-drug antibody testing will be performed. Note: When necessary, samples drawn for one purpose (e.g., immunogenicity) may be used to meet another protocol-defined objective (e.g., DAC HYP concentration assessment).

CONFIDENTIAL

The information contained herein may not be used, disclosed, or published without the written consent of Biogen MA Inc.

14. SCHEDULE OF EVENTS

14.1. Overview

A written, signed Informed Consent Form (ICF) and all authorizations required by local law (e.g., Protected Health Information [PHI] in North America) must be obtained prior to performing any tests or assessments under this protocol.

For subjects entering from Study 205MS301, tests/assessments performed at the subject's last visit in Study 205MS301 and within 28 days of the subject's first dose of DAC HYP (Week 0) in Study 205MS303 may be used as baseline data for Study 205MS303; if final Study 205MS301 tests/assessments are not performed within the 28-day window, they must be repeated upon entry into Study 205MS303 and before the first dose of DAC HYP is administered.

Week 144 Visit of Study 205MS303 will be the Entry Visit for subjects enrolled from Study 205MS203 or Study 205MS302. Any test/assessment done at the subject's last visit in parent studies and within 28 days of the subject's first dose in Study 205MS303 will be used as the baseline and does not need to be repeated at entry into Study 205MS303; test/assessments performed >28 days before the Entry Visit must be repeated at the Entry Visit. Central LFT testing is *mandatory* at Entry Visit.

Clinic visits will occur once every 4 weeks for the first 12 weeks, then every 12 weeks thereafter.

On a dosing day, all tests and assessments must be performed prior to DAC HYP administration. When DAC HYP administration and MRI evaluation are required at the same visit, the MRI scan should be performed prior to DAC HYP administration (Note: MRI scan can be performed up to 4 days prior to the visit).

Before a monthly dose of DAC HYP is given, LFT results (ALT/SGPT, AST/SGOT, alkaline phosphatase, total bilirubin, and GGT only) from prior testing performed within the previous 32 days must be reviewed by the *Study Neurologist* or their backup, and must be within the protocol-required limits.

After Week 12, subjects will have the option of administering DAC HYP at home following Investigator review of monthly pre-dose LFT results. Subjects who are not able to administer their own dose or prefer not to administer their own dose of DAC HYP will be given the option to choose another individual (caregiver) to administer their treatment at home or to have their treatment administered by staff at the study site.

Follow-up visits will take place at 4 (End of Treatment Visit), 8, 12, 16, 20, and 24 weeks after each subject's last dose of DAC HYP. Unscheduled Relapse Assessment Visits (if necessary) should be scheduled within 72 hours of the onset of any new neurological symptoms that may indicate neurological worsening or possible clinical relapse. Unscheduled Hepatic Assessment Visits (if necessary) should be scheduled as soon as possible (but within 1 week) following discontinuation of study treatment due to elevated LFTs. Unscheduled Dermatology Assessment Visits will be performed as per Section 11.7.3.

CONFIDENTIAL

The information contained herein may not be used, disclosed, or published without the written consent of Biogen MA Inc.

Unscheduled PK/■ Visits should be scheduled as soon as possible following significant changes in subjects' medical conditions, as assessed by the Investigator. This visit must be approved by the Biogen Medical Director in advance.

14.2. Site Personnel

For each subject, the Principal Investigator will designate the following study site personnel:

- A primary *Study Neurologist* and backup neurologist
- A primary and backup *Nurse* (or Study Coordinator)
- A primary and backup *Examining Technician*
- An *MRI Technician*
- A *Pharmacist* (or authorized designee)
- A *Study Dermatologist*

The *Study Neurologist* must have a minimum of 2 years of neurology specialty training and anticipate at least a 3-year commitment to the study, or be approved by the study Advisory Committee. The *Study Neurologists* may designate another neurologist at the center who meets the same qualifications to perform the EDSS assessments and other neurologic assessment during the trial. Whenever possible, the EDSS and other neurologic assessments should be performed by the same examiner who performed these assessments in the parent study.

The primary *Study Neurologist* will be responsible for:

- Management of the routine neurological care of the subject
- Assessment (including assignment of causality) and treatment of AEs and MS relapses
- Obtaining an EDSS score based on a detailed neurological examination at the scheduled timepoints required in the protocol, and at every Unscheduled Relapse Assessment Visit
- Review of selected hematology and all blood chemistry results from the central laboratory
- Assessment of LFT results, as detailed in Section 11.7.2
- Monitoring and follow-up of any abnormal hepatic tests
- Referral of subjects to a dermatologist if that subject experiences a mild or moderate cutaneous AE that is associated with more than 1 systemic symptom or sign, a severe cutaneous AE (with or without systemic symptoms or signs), or a serious cutaneous AE (with or without systemic symptoms or signs) as described in Section 11.7.3
- Performing Dermatology Assessments and Physician Global Assessment Scale in subjects with mild or moderate cutaneous AEs (not associated with more than 1 systemic symptom or sign), as detailed in Section 11.7.3

CONFIDENTIAL

The information contained herein may not be used, disclosed, or published without the written consent of Biogen MA Inc.

- Assessment of injection sites, as detailed in [Table 7](#)

Hematology and blood chemistry data will be sent to the investigational sites to aid in management of the subject.

The primary *Nurse* or Study Coordinator will be responsible for:

- Assisting the *Study Neurologist* in subject management, including the treatment of AEs, the treatment and assessment of disease relapses, and the recording of AEs and concomitant medications
- Monitoring the EDSS scores and informing the *Study Neurologist* if a subject experiences at least a 1.0-point increase on the EDSS from a baseline EDSS ≥ 1.0 that is sustained for 24 weeks, or at least a 1.5-point increase on the EDSS from a baseline EDSS < 1.0 that is sustained for 24 weeks
- Administering the patient-reported questionnaires (BDI-II, MSIS-29, EQ-5D), HRU, and subject assessment of injection pain (VAS)
- Collection of blood samples and obtaining vital signs
- Study treatment administration/dispensation/accountability

To ensure consistency across sites, *Examining Technicians* must undergo a standardized training session prior to enrollment of subjects at their site. All sites should attempt to maintain the same *Examining Technician* throughout the study. If an *Examining Technician* has to be replaced, the new *Examining Technician* must undergo a training session. It is not necessary for the *Examining Technician* to be a healthcare professional as long as he/she is qualified, in the opinion of the Principal Investigator, to administer the MSFC (Note: MSFC was administered in this study only until Week 48; therefore, the role of the *Examining Technician* ended after that).

The *MRI Technician* will be responsible for:

- Performing a brain MRI scan with and without Gd at all protocol-required timepoints. Study-specific MRI scan procedures and protocols, which will be provided prior to study start, must be followed.

The *Pharmacist* (or authorized designee) will be responsible for:

- Storage, distribution, and accountability of study treatment.

The *Study Dermatologist* will be responsible for:

- Performing Cutaneous Assessments and Physician Global Assessment Scale in subjects with a mild or moderate cutaneous AE that is associated with more than 1 systemic symptom or sign, a severe cutaneous AE (with or without systemic symptoms or signs), or a serious cutaneous AE (with or without systemic symptoms or signs), as detailed in [Section 11.7.3](#)
- Documenting cutaneous events, as per the protocol.
- Taking photograph(s) of the affected body areas, as required.
- Performing a skin biopsy, as required.

CONFIDENTIAL

The information contained herein may not be used, disclosed, or published without the written consent of Biogen MA Inc.

- Evaluating, treating, and managing mild or moderate cutaneous AEs that are associated with more than 1 systemic symptom or sign, severe cutaneous AEs (with or without systemic symptoms or signs), or serious cutaneous AEs (with or without systemic symptoms or signs), as described in Section 11.7.3.

14.3. Subject Management

The following restrictions apply to all subjects enrolled into this study:

- Subjects must follow the restrictions for concomitant medications and procedures described in Section 11.5.
- Contraception requirements are to be followed as described in Section 15.5.3.
- Whenever possible, a subject should undergo protocol-required tests and assessments at the same time of day throughout the study.
- Subjects should not donate blood until 4 months after their last dose of DAC HYP.
- Subjects should not receive live or live-attenuated vaccines during DAC HYP treatment or for at least 6 months after treatment with DAC HYP.

14.4. Special Instructions for Tests and Assessments

Note: Information about the tests and assessments to be performed in this study is also provided in Section 12 and Section 13, and in the Study Reference Manual.

14.4.1. Rescreening

Subjects who are not eligible for participation at baseline due to a temporary condition (e.g., acute infection) are allowed to be rescreened once the condition has resolved, provided they are rescreened and enrolled within 6 months of completing Study 205MS301, Study 205MS203, or Study 205MS302.

14.4.2. Pregnancy Testing

- Pregnancy testing is only required for women of childbearing potential. A urine pregnancy test is to be performed at the Baseline/Entry Visit and at other timepoints designated in Section 4.2 Schedule of Events. Study treatment will be immediately discontinued if the subject has a positive pregnancy test at any time during the study.
- Results from all urine pregnancy tests must be reviewed by the study site prior to dosing and must be negative.

14.4.3. Liver Function Test Assessments Prior to DAC HYP Dosing

Before a monthly dose of DAC HYP is given, LFT results from prior testing performed within the previous 32 days must be reviewed by the *Study Neurologist* or their backup, and must be within protocol-required limits as described in Section 11.7.2.

LFTs can be performed as follows:

CONFIDENTIAL

The information contained herein may not be used, disclosed, or published without the written consent of Biogen MA Inc.

- Samples for LFTs must be drawn prior to administration of the monthly DAC HYP dose. These samples may be tested either locally inside or outside of the clinic (e.g., at a local laboratory or by visiting nurses) or at the central laboratory at the discretion of the Investigator and the results can then be used to determine whether dosing should continue or be suspended at the monthly dosing timepoint (see Section 11.1).
- If local LFTs have been used to determine whether dosing should continue or be suspended at the time of a scheduled clinic visit, LFTs must also be performed at the central laboratory at the time of the scheduled clinic visit (Note: Scheduled clinic visits occur every 4 weeks during the first 12 weeks of the study and every 12 weeks thereafter).
- If the subject is administering DAC HYP injections at home, site personnel must contact the subject after review of prior LFT results performed within the previous 32 days to authorize the monthly injection, or if LFT results warrant, to instruct the subject to withhold their injection.
- LFTs following a treatment suspension must be performed through the central laboratory until the LFT abnormality is $<2 \times \text{ULN}$. In cases where LFTs cannot be performed via central laboratory, repeat LFT results from local laboratory can be used for confirmation.

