7.2.2. Treatment

Subjects from Study 205MS301 continuing in Study 205MS303 will receive DAC HYP treatment for up to approximately 5 years, or until availability of commercial product (whichever is sooner), under this protocol. Subjects from Study 205MS203 and Study 205MS302 entering Study 205MS303 at Week 144 will have DAC HYP treatment for up to approximately 2 years, or until availability of commercial product (whichever is sooner), under this protocol.

CONFIDENTIAL

The information contained herein may not be used, disclosed, or published without the written consent of Biogen MA Inc.

At the Sponsor's discretion, 75-100 subjects from Study 205MS303 at selected sites may dose with DAC HYP using a single-use autoinjector that contains a PFS on 6 consecutive scheduled dosing days (Table 7).

Eligible subjects will have clinic visits scheduled every 4 weeks for up to Week 12 in this study, followed by clinic visits scheduled every 12 weeks.

Subjects who are dosing at home must be instructed to not administer their monthly dose of DAC HYP until the study site has contacted them to authorize dosing (after the *Study Neurologist* or their backup has reviewed LFT results obtained during the previous 32 days). Subjects need to record the date and time of dosing in their diary if they are dosing at home.

A window of ± 4 days applies to scheduled visits and home dosing.

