11.1. Study Treatment Schedule and Administration

All subjects will receive one DAC HYP 150 mg SC injection every 4 weeks.

DAC HYP will be administered by clinic staff at the monthly visits for the first 12 weeks of this study. After Week 12, administration of DAC HYP may occur in the clinic or at home (by the subject or by a designated caregiver) depending on subject preference. The subject or designated caregiver will be trained by clinic staff on the correct injection technique prior to initiating at-home DAC HYP dosing. **Subjects who are dosing at home must be instructed to not administer their monthly dose of DAC HYP until the study site has contacted them to authorize dosing. A window of ± 4 days applies to home dosing.**

Before a monthly dose of DAC HYP is given, LFT results from a prior test performed within the previous 32 days must be reviewed by the *Study Neurologist* or their backup. Study personnel should promptly inform the subject whether the monthly dose of DAC HYP should be administered or whether study treatment is to be withheld based on the dosing criteria defined in Section 11.7.2. Study personnel will document this communication with the subject. Subjects should administer DAC HYP as soon as permission has been given as per the dosing schedule. Subjects need to record the date and time of dosing in their diary if they are dosing at home.

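### After Week 12, between the 12-weekly visits, the pre-dose liver check caps sample age at 32 days but sets no sampling interval, so one sample can clear two consecutive doses

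*Protocol*

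**What the plan says.** Dosing is monthly: "All subjects will receive one DAC HYP 150 mg SC injection every 4 weeks" (Section 11.1). Visits are not: "Scheduled clinic visits occur every 4 weeks during the first 12 weeks of the study and every 12 weeks thereafter" (Section 14.4.3). A central-laboratory LFT is scheduled at each of those visits (Tables 1, 2 and 4).

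The check before each dose falls to the study neurologist or a backup and is written as a look-back: "Before a monthly dose of DAC HYP is given, LFT results from prior testing performed within the previous 32 days must be reviewed by" one of the two (Section 14.4.3). For home dosing, Section 7.2.2 has the site authorize the injection once the neurologist or "backup has reviewed LFT results obtained during the previous 32 days". Sections 11.1, 11.7.2 and 14.1, the LFT rows of Tables 1, 2 and 4, and the dosing footnotes of Tables 1 to 4 use the same 32 days. None of these places gives an interval between samples or says that a sample may be used only once.

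Two sentences suggest that a test for every dose was meant. Section 14.1: "After Week 12, subjects will have the option of administering DAC HYP at home following Investigator review of monthly pre-dose LFT results". Section 14.4.3: "Samples for LFTs must be drawn prior to administration of the monthly DAC HYP dose".

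Timing is flexible: "A window of ± 4 days applies to scheduled visits and home dosing" (Section 7.2.2).

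**The concern.** A maximum age and a sampling frequency are different rules. If the maximum age exceeds the dosing interval, one sample can serve two doses, and the monthly testing described in Section 14.1 is no longer guaranteed.

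What is at stake is the symptom-free transaminase rise. Section 5.1 lists transaminase elevations and serious hepatic events among the characteristic risks of DAC HYP in Study 205MS301, and reports ALT/AST above 5×ULN in 4% of DAC HYP-treated subjects in Study 205MS201. The suspension rule above 3×ULN and the discontinuation rule for confirmed values above 5×ULN (Sections 11.7.2.1 and 11.7.2.2) act only when a test is done. Between the 12-weekly visits, the pre-dose sample is the only scheduled test that can show a silent rise. Table 5, footnote 1, describes LFT monitoring after the last dose as monthly; the rule that applies on drug does not secure as much.

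**Working it through.** **Inputs, all from the protocol.** Dosing interval 28 days (Section 11.1). Maximum sample age 32 days (Section 14.4.3). Window ±4 days for visits and home doses (Section 7.2.2). Central LFT at every visit, 12-weekly after Week 12 (Tables 1, 2 and 4). Last dose at Week 236, since the Week 240 visit falls 4 weeks after it (Table 4).

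**Assumption.** The protocol states no turnaround for LFT results. Let *t* be the number of days from draw to usable result; *t* = 0 is a same-day result.

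**The 32 days.** 28 + 4 = 32, one dosing interval plus one window. The figure is reproducible, although the protocol does not give this derivation.

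**Can one sample clear two doses?** A sample drawn *a* days before dose *n* is 28 + *a* days old at dose *n*+1. It clears both if *a* ≥ *t* and 28 + *a* ≤ 32, that is, *t* ≤ *a* ≤ 4. So reuse is possible for turnaround of 0 to 4 days and impossible at 5 days or more, at 28-day spacing. With the windows, consecutive doses lie 28 − 8 = 20 to 28 + 8 = 36 days apart; a dose-day sample clears the next dose only when the spacing is 32 days or less.

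**Can it clear three?** Two dosing intervals span at least 56 − 8 = 48 days, which exceeds 32. No.

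**Longest gap at nominal timing.**
- Dose-day draws: the Week 12 visit sample (day 84) clears day 84 and day 112. The next draw is on day 140. Gap 140 − 84 = 56 days.
- Draw 4 days early: a sample on day 108 clears day 112 (age 4) and day 140 (age 32). The next sample is at the Week 24 visit, day 168, with a same-day result. Gap 168 − 108 = 60 days.
- In general the gap is 32 + 28 − *t*: 60, 59, 58, 57, 56 for *t* = 0 to 4.

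**Longest gap using the windows fully.** Doses on days 108 and 136 (each 4 days early), Week 24 visit on day 172 (4 days late), sample on day 104. Age at day 136 is 32. Gap 172 − 104 = 68 days. In general 32 + 36 − *t*: 68 down to 64 for *t* = 0 to 4.

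**Fewest samples, 205MS301 subjects.** Doses from Week 12 to Week 236: (236 − 12)/4 + 1 = 57. Visits from Week 12 to Week 228: (228 − 12)/12 + 1 = 19. Each 12-week block has three doses and needs the visit sample plus one other: 19 + 19 = 38 samples for 57 doses, against 57 at one per dose.

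**Would a ban on reuse be enough?** No. Samples on days 84, 108 and 168 can each authorize one dose (days 112, 140 and 168, at ages 28, 32 and 0), with the Week 12 dose cleared by a separate local test. The gap is still 60 days. The same pattern with windows (samples on days 80, 104 and 172) gives 68. An interval rule is needed as well.

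**With an interval anchored to the nominal dosing date, ±4 days.** The longest gap is 28 + 4 + 4 = 36 days.

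**The case against.** The best reply is that the 32-day limit does not stand alone. Section 14.4.3 ties a draw to the monthly dose, and Section 14.1 speaks of monthly pre-dose results; taken together, the natural reading is one test per dose with 32 days as tolerance. That stands as evidence of intent. It does not close the gap, because a sample drawn before one dose was also drawn before the next, and no sentence excludes using it again.

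The second reply is that the figures are extremes. That stands too. The count of 38 needs a site to omit one draw in every block, and 68 days needs an early draw, two early doses, a late visit and same-day results.

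The third is that safeguards remain. Subjects with a significant change in medical status should not dose until evaluated (Section 11.7), hepatic signs or symptoms require prompt transaminase testing (Section 11.7.2), and central LFTs continue every 12 weeks. This confines the exposure to silent rises between visits.

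A reader might go further and infer that subjects will in practice be tested only every two months. Nothing in the protocol shows that sites would sample this way. A reader might also extend the counts to subjects entering at Week 144 from Studies 205MS203 and 205MS302. Table 4, footnote 3, gives them 12-weekly visits, but Section 7.2.2 says "Eligible subjects will have clinic visits scheduled every 4 weeks for up to Week 12 in this study" without separating cohorts. Which governs is unclear, so no count is given for them.

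**Conclusion.** The point holds as a weakness in the operative rule; it should be fixed. For 205MS301 subjects after Week 12, between the 12-weekly central LFTs, the protocol followed exactly permits 56 to 60 days on drug without an LFT at nominal timing, and up to 68 days with the windows fully used, where monthly testing is evidently intended. These are compliant maxima. They rest on a result turnaround of 4 days or less, which the protocol does not state; 60 and 68 need same-day results. Testing up to Week 12 is fixed for these subjects and is not affected.

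The documents do not support the stronger statement that the protocol asks for nothing beyond a sample age, since Sections 14.1 and 14.4.3 link testing to the monthly dose. Nor would a 28 ± 4-day rule hold the gap to 32 days at no extra testing: visits within their windows can be 36 days apart, so a rule counted from sample to sample would force extra draws, and one anchored to the schedule allows 36 days.

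**What to change.** Add to Section 14.4.3: *An LFT sample must be drawn every 4 weeks on the dosing schedule (±4 days, anchored to the nominal dosing date); one sample may authorize only one dose; and the sample must be no more than 32 days old at dosing.* Mirror it in Sections 7.2.2, 11.1, 11.7.2 and 14.1, in the LFT rows and footnotes of Tables 1, 2 and 4, and in the dosing footnote of Table 3.

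All three clauses are needed: the interval limits the gap to 36 days, the single-use clause stops reuse, and the age limit keeps the result current. Where a local result can be back in time, the sample should preferably be drawn after the preceding dose, because the sentence alone does not require that.

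The cost is one sentence and its copies. Sites lose the flexibility to reuse a sample, and an occasional additional local draw may be needed when visits or doses fall at opposite ends of their windows. The superseded Version 3 schedule in the same file asked for testing every 28 ± 4 days. That suggests that a stated interval is workable; the difference between versions is not itself an error.
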